Target vessel revascularization is any repeat percutaneous intervention of the target vessel or bypass surgery of the target vessel.

[Target Lesion Revascularization (TLR)]

Target lesion revascularization is defined as any repeat percutaneous intervention of the target lesion or bypass surgery of the target vessel.

[Clinically-Indicated Revascularization (CI-TLR/TVR)]

Revascularization will be considered ischemia-driven if the target lesion diameter stenosis is $\geq 50\%$ by QCA and any of the following criteria for ischemia are met:

- Positive functional ischemia study including positive FFR/iFR corresponding to the area served by the target lesion; or
- Ischemic ECG changes at rest in a distribution consistent with the target vessel; or
- Typical ischemic symptoms referable to the target lesion; or
- IVUS of the target lesion with a minimal lumen area (MLA) of $\leq 4\text{mm}^2$ for non left main lesions or $\leq 6\text{mm}^2$ for left main lesions. If the lesions are de novo (i.e. not restenotic), the plaque burden must also be $\geq 60\%$; or
- FFR of the target lesion ≤ 0.80 or iFR of the target lesion ≤ 0.89 .

A target lesion revascularization for a diameter stenosis less than 50% might also be considered ischemia-driven by the Clinical Events Committee if there was a markedly positive functional study or ECG changes corresponding to the area served by the target lesion.

STENT THROMBOSIS

(ARC)⁴²

Stent thrombosis should be reported as a cumulative value at the different time points and with the different separate time points. Time 0 is defined as the time point after the guiding catheter has been removed and the patient left the catheterization lab.

Timing:

- Acute stent thrombosis*: 0 - 24 hours post stent implantation
- Subacute stent thrombosis*: >24 hours - 30 days post stent implantation
- Late stent thrombosis†: 30 days - 1 year post stent implantation
- Very late stent/ thrombosis†: >1 year post stent implantation

* Acute/subacute can also be replaced by early stent thrombosis. Early stent thrombosis (0 - 30 days) - this definition is currently used in the community.

† Including “primary” as well as “secondary” late stent thrombosis; “secondary” late stent thrombosis is a stent thrombosis after a target segment revascularization.

Categories:

- Definite
- Probable
- Possible

Definitions of each category are as follows.

- **Definite stent thrombosis**

Definite stent thrombosis is considered to have occurred by either angiographic or pathologic confirmation.

Angiographic confirmation of stent thrombosis*

The presence of a thrombus[†] that originates in the stent or in the segment 5 mm proximal or distal to the stent and presence of at least one of the following criteria within a 48-hour time window:

- Acute onset of ischemic symptoms at rest
- New ischemic ECG changes that suggest acute ischemia
- Typical elevation or depression in cardiac biomarkers (refer to definition of spontaneous MI)
- Nonocclusive thrombosis

- Thrombus Intracoronary thrombus is defined as a (spheric, ovoid, or irregular) noncalcified filling defect or lucency surrounded by contrast material (on 3 sides or within a coronary stenosis) seen in multiple projections, or persistence of contrast material within the lumen, or a visible embolization of intraluminal material downstream.
- Occlusive thrombus
 - TIMI 0 or TIMI 1 in-stent or proximal to a stent up to the most adjacent proximal side branch or main branch (if originates from the side branch).
- * The incidental angiographic documentation of stent occlusion in the absence of clinical signs or symptoms is not considered a confirmed stent thrombosis.
- † Intracoronary thrombus.

Pathological confirmation of stent thrombosis

Evidence of recent thrombus within the stent determined at autopsy or via examination of tissue retrieved following thrombectomy.

- **Probable stent thrombosis**

Either of the following occurred after stent implantation will be considered a probable stent thrombosis:

- Any unexplained death within the first 30 days[‡]
- Irrespective of the time after the index procedure, any MI* that is related to documented acute ischemia in the territory of the implanted stent without angiographic confirmation of stent thrombosis and in the absence of any other obvious cause

‡ For studies with ST-elevation MI population, one may consider the exclusion of unexplained death within 30 days as evidence of probable stent thrombosis.

- **Possible stent thrombosis**

Clinical definition of possible stent thrombosis is considered to have occurred with any unexplained death from 30 days following intracoronary stenting until end of trial follow up.

STROKE

All strokes with stroke severity of Modified Rankin Scale (mRS) ≥ 1 will be included in the primary endpoint. Stroke severity will be classified using an adaptation of the modified Rankin Scale (www.strokecenter.org/trials/scales/rankin.html) as follows:

Scale	Disability
0	No stroke symptoms at all. (May have other complaints)
1	No significant disability despite persistent stroke symptoms. Able to carry out all usual duties and activities
2	Slight disability. Unable to carry out usual activities, but able to look after affairs without assistance. Could live alone.
3	Moderate disability. Requiring some help, but able to walk without assist (of a person). Can be left alone for a few days.
4	Moderate to severe disability. Unable to walk without assist (of a person). Unable to attend to own bodily needs without assist. Could be left alone for a few hours of a day.
5	Severe disability. Bedridden, incontinent, and requiring constant nursing care and attention and 24 hour supervision.
6	Dead.
	Stroke: Modified Rankin score ≥ 1

Strokes may be further sub-classified as follows:

1. **Ischemic** (Non-hemorrhagic): a stroke caused by an arterial obstruction due to either a thrombotic (e.g., large vessel disease/atherosclerotic or small vessel disease/lacunar) or embolic etiology.

2. **Hemorrhagic**: a stroke due to a hemorrhage in the brain as documented by neuroimaging or autopsy. This category will include strokes due to primary intracerebral hemorrhage (intraparenchymal or intraventricular), ischemic strokes with hemorrhagic transformation (i.e., no evidence of hemorrhage on an initial imaging study but appearance on a subsequent scan), subdural hematoma,* and primary subarachnoid hemorrhage.

*All subdural hematomas that develop during the clinical trial should be recorded and classified as either traumatic versus nontraumatic.

3. **Unknown**: the stroke type could not be determined by imaging or other means (e.g., lumbar puncture, neurosurgery, or autopsy) or no imaging was performed.

Transient Ischemic Attack (as compared to stroke) is defined as:

- New focal neurologic deficit with rapid symptom resolution, usually 1-2 hours, always within 24 hours
- Neuroimaging without tissue injury

18 APPENDIX II: IVUS AND IFR (FFR) RECOMMENDATIONS³**Pre-revascularization assessment of intermediate distal ULMCA Lesions****1. Prior to Randomization**

The presence of significant lesion(s) in any of the left main bifurcation segments (i.e., distal left main, ostial LAD or ostial LCX) must be confirmed by the academic core lab (Cardialysis B.V., Rotterdam, NL) using dedicated bifurcation QCA software.

If the distal ULMCA lesion is deemed insignificant, the lesion should in most cases not be treated unless, for example, treatment of an ostial LAD or ostial LCX lesion necessitates left main treatment (left main equivalence), or the lesion is irregular or otherwise disrupted (i.e., Medina 011 or 010). PCI of other lesions should be performed as clinically indicated.

Pre-procedure iFR is mandatory to explore the physiological importance of the left main bifurcation.

1a. IVUS Criteria

IVUS criteria to defer revascularization is a distal ULMCA minimum lumen area (MLA) $>6.0 \text{ mm}^2$ ⁴⁵. Conversely, if the left main MLA is $\leq 6.0 \text{ mm}^2$, the distal ULMCA lesion may be considered to be hemodynamically significant and considered equivalent to the core lab DS $\geq 50\%$.. In order to determine the true MLA, it may be necessary to image back to the aorto-ostial junction from both the LAD and LCX; the smaller of the two MLAs is the more accurate and should be used for decision-making. Practically, however, this is only necessary if the first pullback shows an MLA $>6.0 \text{ mm}^2$.

[figure not shown]
1b. FFR /iFR Criteria

Deferral of borderline distal left main lesions with a negative FFR has been demonstrated to be safe.⁴⁶ In the present study, the FFR criteria used to defer revascularization of the distal ULMCA is an FFR >0.80 .^{47, 48} This is most useful if there are no other lesions in both the LAD and LCX (otherwise there may be false positive and false negative FFR measurements in the ULMCA). The pressure wire transducer should be positioned just distal to distal ULMCA lesion and proximal to any secondary lesions, as long as there is a major branch after the left main which appears angiographically nearly normal for adequate runoff (e.g. the LAD or a large diagonal).

Although scarce data of iFR usage in left main are available, the same considerations may be applied for iFR with a cut-off of 0.89.

For a detailed iFR acquisition protocol please refer to Appendix III.

Note: See figure below. If there is also a tight stenosis in the proximal LAD distal to the ULMCA bifurcation lesion, and the FFR transducer is placed between these lesions, FFR may be false negative (>0.80); if the transducer is placed distal to a second hemodynamically significant lesion, the FFR may be false positive (≤ 0.80); therefore, IVUS evaluation is strongly preferred.

IVUS for PCI Guidance of distal ULMCA PCI

The use of IVUS to guide distal ULMCA intervention is strongly recommended as a publication describing the results of a large non randomized but adjusted registry suggests that 3-year mortality may be improved with IVUS-guided DES implantation of the (distal) ULMCA.⁴⁹ In patients in whom IVUS is used to guide PCI, it is strongly recommended that both the LAD

and LCX be imaged *prior to* intervention back to the aorto-ostial junction to assist with stent size and length selection. If the distal ULMCA disease extends into the ostial/proximal LAD (as it does in the majority of subjects), it is recommended that stent length be selected so as to end the stent in a segment of LAD with a plaque burden <50%. With cross-over technique, a preprocedural minimal lumen area (MLA) of <3.7 mm² within the LCX ostium as well as pre-procedural plaque burden of >56% at the LCX ostium were predictive of a poststenting FFR <0.80.⁵⁰ While there are no IVUS criteria for selecting a one-stent (cross-over) vs. a two-stent strategy, in general a LCX ostium lumen area >4.0 mm² or a plaque burden ≤60% in a short segment of disease may indicate that a one-stent (cross-over) strategy will be adequate.

Iterative IVUS and post-dilation should be performed until the distal ULMCA minimum stent area is >8.5mm² and the ostial/proximal LAD minimum stent area is at least >6.0mm² and preferably matched to the distal reference vessel diameter if larger. Observational data in non-LMCA lesions has shown that in general the larger the minimal stent area the lower the likelihood of restenosis and stent thrombosis^{18, 51-53} and thus post-dilation with non compliant balloons sized up to 0.25-0.50 mm less than the IVUS determined true vessel diameter (average media-media dimension) to safely achieve the largest maximal luminal dimension is recommended. It is strongly recommended that IVUS is also performed post-stenting from at least one epicardial coronary artery, usually the LAD, with pullback into the aorta (disengaging the guide to ensure the ostium is not missed). If a 1-stent technique is used (most commonly from the ULMCA into the LAD, “crossing over” the LCX), it is desirable but not mandatory that the ostial LCX also be imaged post-intervention if possible. If a 2-stent technique is used, IVUS pullback across the LAD and LCX is strongly recommended if the IVUS catheter passes easily into the LCX. *LCX or side branch imaging should not be pursued aggressively to avoid IVUS related (or pressure wire-related) complications.* If the IVUS catheter or pressure wire can be safely positioned into the LCX, then, in general, an LCX ostium lumen area >4.0mm² (single stent strategy) or >5.5mm² (two stent strategy) or an FFR >0.80 (single stent strategy) indicates that no further intervention is necessary.^{18, 51-53}

Severe dissections present by IVUS (residual true lumen within the dissection flap below the above-mentioned criteria in each segment [LM: 8.5 mm², LAD: 6.0 mm², LCX: 5.5 mm²]) should in general receive an additional stent. Malapposition with stent area below the above-mentioned cut-off criteria in respective segment should in general be treated by additional post-dilatation with larger balloons.

IVUS and iFR for Guidance of other lesion (non-distal ULMCA PCI)

Pre-intervention non-distal ULMCA lesion assessment

To avoid unnecessary interventions with subsequent peri-procedural and late myocardial infarctions and repeat revascularization procedures⁵⁴ PCI of non ischemia producing lesions should in general not be performed. Whereas IVUS is strongly recommended (preferable to FFR) to assess intermediate ULMCA stenoses, it is just as strongly recommended that iFR be performed (preferable to IVUS) in all intermediate non-LMCA lesions (those with an angiographic diameter stenosis <70% by visual estimate), unless there is a positive nuclear or echocardiographic noninvasive study with ischemia clearly present in the distribution of that lesion. In the setting of serial stenoses, stenting should only be performed if the iFR beyond all narrowings is ≤ 0.89 (or FFR ≤ 0.80 if available).⁵⁵ . After stenting the first lesion, iFR is measured again and any residual narrowing causing an iFR ≤ 0.89 (or FFR ≤ 0.80 if available) is stented. (.). For sites that do not use FFR/iFR, it is strongly recommended that pre-interventional IVUS is used in all intermediate lesions (those with a visually estimated angiographic stenosis of <70% (unless there is a positive nuclear or echocardiographic noninvasive study with ischemia clearly present in the distribution of that lesion). A significant lesion by IVUS criteria that should be stented has both a minimal luminal area (MLA) of ≤ 4 mm² and a plaque burden of >60%. In the absence of extenuating circumstances (e.g. plaque rupture, etc.), lesions that do not have both of these criteria should not undergo PCI.

Although scarce data of iFR usage in left main are available, the same considerations may be applied for iFR with a cut-off of 0.89.

IVUS guidance of non-ULMCA stenting

If IVUS is used to guide treatment of ULMCA lesions, it is recommended that IVUS also be used to guide treatment of important non-LMCA lesions in the LAD, LCX, and RCA circulations. XIENCE stent size and length should be selected and optimized to achieve a minimum stent area >5.5 mm² in non ULMCA lesions (with post-dilation with non compliant balloons sized up to 0.25-0.5mm less than the IVUS determined true vessel diameter (average media-to-media dimension), and to end the stents in arterial segments with a plaque burden <50%. Severe dissections present by IVUS (residual true lumen within the dissection flap ≤ 5.5 mm² either proximal or distal to the stent) should in general receive an additional stent. Malapposition with stent area ≤ 5.5 mm² should in general be treated by additional post-dilatation with larger balloons.

Follow-up

Since the site of restenosis after distal ULMCA bifurcation intervention is typically the ostium of the LCX, and since many presumed ostial LCX restenoses are angiographic artifacts (i.e. appear angiographically severe, but in fact are not hemodynamically significant),⁵⁶ it is strongly recommended that FFR/iFR be performed before treating any presumed restenotic lesions in the ostial LCX location (regardless of angiographic severity, unless totally occluded) unless there is unequivocal lateral wall ischemia by nuclear or echocardiographic noninvasive testing. If the FFR is >0.80 or iFR > 0.89 , the ostial LCX lesion should not be treated and, thus, TLR (and possible procedural complications) avoided. For sites that do not use FFR/iFR, it is strongly recommended that pre-interventional IVUS of the ostial LCX be performed instead with an MLA $>4.0\text{mm}^2$ used as the criteria to defer intervention and avoid TLR⁵⁷. Similarly, prior to performing a repeat intervention elsewhere in the coronary tree, if the visually assessed angiographic diameter stenosis is $<70\%$, ischemia should be documented according to either a positive nuclear or echocardiographic noninvasive test in the distribution of the recurrent lesion, or an FFR ≤ 0.80 /iFR ≤ 0.89 , or IVUS with a MLA $\leq 4.0\text{ mm}^2$.

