5 ENDPOINTS

5.1 Primary Endpoint

The primary endpoint for this trial is defined as the patient-oriented composite endpoint (PoCE) at 12 months post-procedure. PoCE is a composite measure of

- All-cause mortality
- Stroke (modified Rankin Scale (mRS≥1)
- Any Myocardial Infarction* (includes nontarget vessel territory)
- Any unplanned revascularization for ischemia (includes all target and nontarget vessels)

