5.2 Secondary Endpoints at all follow-up visits/contacts

1. Composite Endpoints

- Patient Oriented Composite Endpoint (PoCE) defined as the composite of all-cause death, stroke, any MI*, and any revascularization (for all follow-up contacts other than 12 months)
- Target Vessel Failure (TVF) defined as cardiac death, TV MI*, and clinically indicated target vessel revascularization
- TLF (DoCE) defined as cardiac death, TV MI* and clinically-indicated target lesion revascularization (DoCE will be reported both including the left-main target lesion only and all target lesions)

2. Mortality

- All death
- Cardiac death
- Non-cardiac death (vascular and non-cardiovascular)

3. Stroke

- All
- Ischemic
- Hemorrhagic

4. Myocardial Infarction*

- All MI (periprocedural, spontaneous, Q-wave and non Q-wave),
- Target Vessel/ Non-Target Vessel MI

5. Revascularization

- Any revascularization
- Target Lesion revascularization (TLR) (any, clinically-indicated TLR, non-clinically indicated TLR) TLR will be reported both including the left-main target lesion only and all target lesions)
- Target Vessel revascularization (TVR) (any, clinically-indicated TVR, non-clinically indicated TVR)
- Non-Target Vessel revascularization

6. Stent thrombosis according to ARC classification

* Definition EXCEL study (APPENDIX I: Definitions)

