6.1 Inclusion Criteria

1. Patient has distal unprotected Left-Main coronary artery (ULMCA) disease with angiographic diameter stenosis (DS) $\geq 50\%$ (confirmed by off-line QCA, using dedicated QCA bifurcation software by academic core lab) with documented ischemia or FFR ≤ 0.80 (following ESC guidelines, IA recommendation, for revascularization in patients with stable angina or silent ischemia) requiring revascularization. In case pre-procedural IVUS is available a left main MLA $\leq 6.0\text{mm}^2$ is considered equivalent to the core lab DS $\geq 50\%$).
2. Left-Main Medina classification 100, 110, 101, 011, 010, 111 confirmed by on-line or off-line QCA, using dedicated QCA bifurcation software
3. Clinical and anatomic eligibility for PCI as agreed by the local Heart Team including anatomic SYNTAX Score (<33).
4. Left main vessel diameter ≥ 3.0 mm and ≤ 4.5 mm, and main branch vessel diameter ≤ 3.75 mm, measured by visual assessment. All target lesions must be located in a native coronary artery.
5. Patient with silent ischemia, chronic stable angina or stabilized acute coronary syndromes with normal cardiac biomarker values

Note: For patients showing elevated Troponin (e.g. non-STEMI patients) at baseline (within 24h pre-PCI) an additional blood sample must be collected prior to the PCI procedure to confirm that:

- hs-cTn or Troponin I or T levels are stable, i.e. the value should be within 20% range of the value found in the first sample at baseline, or have dropped
- CK-MB and CK levels are within normal range

If hs-cTn or Troponin I or T levels are stable or have dropped, the CK-MB and CK levels are within normal ranges, and the ECG is normal, the patient may be included in the study.

6. Male or female patients ≥ 18 years
7. Able to understand and provide informed consent and comply with all study procedures including follow-up

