Platelet transfusions should be recorded and reported but are not included in these definitions until further information is obtained about the relationship to outcomes.

If a CABG-related bleed is not adjudicated as at least a type 3 severity event, it will be classified as not a bleeding event. If a bleeding event occurs with a clear temporal relationship to CABG (i.e., within a 48-h time frame) but does not meet type 4 severity criteria, it will be classified as not a bleeding event.

*Corrected for transfusion (1 U packed red blood cells or 1 U whole blood = 1 g/dL hemoglobin).

†Cell saver products are not counted.

CABG indicates coronary artery bypass graft

DEATH

(ARC)⁴²

The deaths will be adjudicated per the ARC definition: All deaths are considered cardiac unless an unequivocal non-cardiac cause can be established. Specifically, any unexpected death even in patients with coexisting potentially fatal non-cardiac disease (e.g. cancer, infection) should be classified as cardiac.

- **Cardiac death:**

Any death due to proximate cardiac cause (e.g. MI, low-output failure, fatal arrhythmia), unwitnessed death and death of unknown cause, all study procedure related deaths including those related to concomitant treatment.

- **Vascular death:**

Death due to non-coronary vascular causes such as cerebrovascular disease, pulmonary embolism, ruptured aortic aneurysm, dissecting aneurysm, or other vascular cause.

- **Non-cardiovascular death:**

Any death not covered by the above definitions such as death caused by infection, malignancy, sepsis, pulmonary causes, accident, suicide or trauma.

MYOCARDIAL INFARCTION (MI)

EXCEL study definition

Peri/Post procedure MI:

Defined as the occurrence within 72 hours after PCI of either:

- CK-MB $\geq 10x$ ULN or cTn* (I or T) $\geq 70x$ ULN,
- OR: CK-MB $\geq 5x$ ULN or cTn* (I or T) $\geq 35x$ ULN in combination with any of the following:
 - new pathological Q waves in at least 2 contiguous leads or new persistent non-rate related LBBB, or
 - angiographically documented native coronary artery occlusion or new severe stenosis with thrombosis and/or diminished epicardial flow, or
 - imaging evidence of new loss of viable myocardium or new regional wall motion abnormality

*while EXCEL definition did not comprise cTn, we consider equivalence CK-MB $\geq 10x$ versus cTn $\geq 70x$ and CK-MB $\geq 5x$ versus cTn $\geq 35x$ ⁴³

Spontaneous MI*

Defined as the occurrence >72 hours after any PCI of:

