In instances of myocardial injury with necrosis where a condition other than CAD contributes to an imbalance between myocardial oxygen supply and/or demand, e.g. coronary endothelial dysfunction, coronary artery spasm, coronary embolism, tachy-/brady-arrhythmias, anemia, respiratory failure, hypotension, and hypertension with or without LVH.

MI type 3: MI resulting in death when biomarker values are unavailable

Cardiac death with symptoms suggestive of myocardial ischemia and presumed new ischemic ECG changes or new LBBB, but death occurring before blood samples could be obtained, before cardiac biomarker could rise, or in rare cases cardiac biomarkers were not collected.

MI type 4a: MI related to PCI (<48 hours post PCI)

Adjudicated per EXCEL/SCAI definition only, see above.

MI type 4b: MI related to stent thrombosis

Myocardial infarction associated with stent thrombosis is detected by coronary angiography or autopsy in the setting of myocardial ischemia and with a rise and/or fall of cardiac biomarkers values with at least one value above the 99th percentile URL.

MI type 4c: MI related to restenosis

Myocardial infarction in the presence of restenosis defined as $\geq 50\%$ stenosis at coronary angiography or a complex lesion associated with a rise and/or fall of cTn values $> 99\text{th}$ percentile URL and no other significant obstructive CAD of greater severity following:

- Initially successful stent deployment ($< 30\%$ stenosis), OR
- Initially successful dilatation of a coronary stenosis with balloon angioplasty ($< 50\%$)

MI type 5: MI related to CABG (<48 hours post CABG)

Adjudicated per EXCEL definition only, see below.

PERI-PROCEDURAL MYOCARDIAL INFARCTION (SCAI 2013)⁴³

Peri-procedural MI according to SCAI 2013 definition

Peri-procedural MI after PCI or CABG (<48 hours post- PCI or CABG)

For patients with normal baseline cardiac biomarkers: any of the following criteria:

- CK-MB $\geq 10 \times \text{ULN}$ or cTn (I or T) $\geq 70 \times \text{ULN}$
- OR: CK-MB $\geq 5 \times \text{ULN}$ or cTn (I or T) $\geq 35 \times \text{ULN}$ in combination with any of the following:
 - New pathologic Q-waves in ≥ 2 contiguous leads
 - OR: new persistent LBBB

For patients with elevated baseline cardiac biomarkers: any of the following criteria:

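### The primary-endpoint MI rule counts a troponin of at least 70x ULN after PCI with no baseline correction, although patients may enrol with elevated troponin

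*Combined protocol and SAP*

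**What the plan says.** Section 5.1 includes "Any Myocardial Infarction* (includes nontarget vessel territory") in the composite. The asterisk, explained in the synopsis and in Section 5.2, leads to "Definition EXCEL study (APPENDIX I: Definitions").

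In Appendix I, under the EXCEL study definition, peri-procedural MI is "Defined as the occurrence within 72 hours after PCI of either" of two tiers:

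- The first is "CK-MB $\geq 10x$ ULN or cTn* (I or T) $\geq 70x$ ULN", with nothing further required.
- The second halves both thresholds (5x and 35x) but adds a new ECG, angiographic or imaging finding.

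A footnote says that the troponin values are this protocol's addition: "while EXCEL definition did not comprise cTn, we consider equivalence". It cites reference 43, the SCAI consensus document.

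The same appendix later reproduces the SCAI definition under that reference. There the absolute thresholds apply to patients with normal baseline markers. A separate block begins "For patients with elevated baseline cardiac biomarkers: any of the following criteria". Where the baseline is stable or falling, it requires a rise of at least 10x ULN (CK-MB) or 70x ULN (troponin) over the previous nadir.

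The note to inclusion criterion 5 (Section 6.1, repeated in the synopsis and Section 7.2) provides for raised troponin at entry: "For patients showing elevated Troponin (e.g. non-STEMI patients) at baseline (within 24h pre-PCI) an additional blood sample must be collected". Such patients may enter if troponin "levels are stable or have dropped, the CK-MB and CK levels are within normal ranges", and the ECG is normal. Stable means within 20% of the first sample. No upper limit on the troponin level is given.

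**The concern.** The 70x limb looks only at the level reached after PCI. In a patient who arrives with a high troponin, that level may reflect the earlier event and not the procedure. The plan admits such patients and holds the information needed to separate the two cases, because pre-PCI samples are mandatory. Yet the rule that feeds the primary endpoint does not use it. The normal CK-MB required at entry protects the CK-MB limb but not the troponin limb, since the two are joined by a plain 'or'.

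The result is judged against a fixed target, and Section 3 rests the design on definitions similar to EXCEL's. Events that reflect only the baseline would raise the observed rate with no matching events in the benchmark, because by the plan's own footnote EXCEL did not use troponin. With power set at 80%, there is little room for them.

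**Working it through.** **1. The two rules side by side**

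These are hypothetical patients with stable or falling troponin before PCI, and no other finding.

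| Last pre-PCI troponin | Post-PCI troponin | Increment | Primary-endpoint rule (at least 70x) | SCAI rule (baseline + 70x) |
|---|---|---|---|---|
| 80x ULN | 80x ULN | 0 | MI | needs 150x: not MI |
| 100x ULN | 75x ULN | negative | MI | needs 170x: not MI |
| 50x ULN | 70x ULN | 20x | MI | needs 120x: not MI |

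The rules disagree in every row. The only link between them is the type 4a line of the Third Universal Definition table, which names EXCEL and SCAI together and gives no order of precedence.

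**2. The plan's sample size**

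Inputs from Sections 8.1 and 8.2: expected rate p1 = 0.167; margin 0.063, so target p0 = 0.167 + 0.063 = 0.230; one-sided alpha 5%; power 80%.

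n = [(z0.95·√(p0(1−p0)) + z0.80·√(p1(1−p1))) / (p0−p1)]²
= [(1.645·√(0.23·0.77) + 0.842·√(0.167·0.833)) / 0.063]²
= [(0.6922 + 0.3139) / 0.063]² = 255.04, rounded up to **256**, as stated.

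At the planned enrolment of 260, the exact binomial rule is success with at most 48 events (actual alpha 0.045), and power is P(X ≤ 48 | 0.167) = 80.2%.

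Section 8.1 instead plans a normal-approximation upper bound on the Kaplan-Meier estimate. Without censoring, success needs p̂ + 1.645·√(p̂(1−p̂)/260) < 0.23. With 49 events the bound is 0.2284 (success); with 50 it is 0.2325 (failure). Power is P(X ≤ 49 | 0.167) = 84.4%. Part of that advantage comes from an actual alpha of 0.062, which is a separate matter.

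**3. What false events would cost**

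The documents do not say how many patients will enrol with elevated troponin, how many will be at or above 70x, or how many will have troponin drawn after PCI. The added rates below are therefore assumptions. Each added event must fall in a patient with no other composite event. Power is recomputed at 0.167 plus the added rate, n = 260.

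| Added to the 16.7% rate | Exact test | Planned bound, no censoring |
|---|---|---|
| 0 | 80.2% | 84.4% |
| 1/260 = 0.38 points | 75.2% | 80.0% |
| 0.5 points | 73.6% | 78.6% |
| 1 point | 66.2% | 71.8% |
| 2 points | 49.9% | 56.2% |

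The stated sample size of 256 does not depend on the correction.

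**The case against.** The best reply is that the route is nearly closed.

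- **Assay.** Section 1.1 (note 6) and Section 7.8 prefer CK-MB after PCI and turn to troponin only where CK-MB is unavailable. Patients with elevated troponin must have had CK-MB measured to enter, so their sites can run it. This stands and narrows the reach considerably. It does not close the gap: it is a sampling rule and not an adjudication rule, and Section 7.8 also calls for troponin or CK-MB after any adverse cardiac event.
- **Population.** Inclusion 5 itself asks for normal markers, and exclusion 10 removes recent MI with markers still raised. By the plan's own equivalence, a troponin of 70x beside a normal CK-MB is discordant. This too narrows the group. But these criteria conflict with the note that admits raised troponin, so they cannot be relied on to exclude it.
- **The 35x tier.** A reader might infer that it is exposed as well. It is not: it needs a new ECG, angiographic or imaging finding, which an unchanged marker level alone cannot supply.
- **Adjudication.** The committee's charter (Section 11.3) may settle the matter, and it is not among the documents. However, the committee must classify by the protocol's definitions, so the protocol is where the rule belongs.
- **Size.** A reader might infer a large loss of power. Suppose 5-10% enrol with elevated troponin and 10-20% of those are misclassified: that gives 0.5 to 2.0 points, or 0.42 to 1.67 points after multiplying by 0.833 for patients without another event. None of these inputs has a source in the documents. If only 2% are misclassified, the expected number is 260 × 0.833 × 0.05 × 0.02 = 0.2 to 260 × 0.833 × 0.10 × 0.02 = 0.4 patients, and power under the planned bound is 83.5% to 82.6%.

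**Conclusion.** The point holds as a gap in the endpoint definition. The primary rule borrows absolute troponin thresholds from a source that, as reproduced in this protocol, limits them to normal baselines. It applies them to a trial that admits elevated baselines and states no precedence between the two texts. The exposure is confined to the stand-alone 70x limb, in patients with elevated pre-PCI troponin whose post-PCI troponin is measured and counted.

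The size is illustrative only. One expected false MI in 260 would cost about 5 points of exact-test power (80.2% to 75.2%) or about 4 under the planned bound without censoring (84.4% to 80.0%). The documents do not show that even one will occur.

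A reader might also infer that the trial could wrongly succeed. The documents do not support that: false MIs only raise the rate against a fixed 23.0% target, so this bias works against the device and does not inflate type I error. Whether there should be a troponin limb at all, given that EXCEL had none, is a separate question that the protocol discloses.

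**What to change.** Add one sentence to the EXCEL definition in Appendix I and carry it into the Clinical Event Committee charter: in patients with elevated pre-PCI troponin, peri-procedural MI for the primary endpoint is adjudicated on CK-MB; where only troponin is available, it is adjudicated on the increment over the pre-PCI value set out in the SCAI text of the same appendix.

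Separately, reconcile the note to inclusion 5 with that criterion's own requirement of normal markers and with exclusion 10, so that it is clear whether and when these patients may enter.

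The cost is one sentence and slightly more adjudication work. The pre-PCI samples are already required, and the sample size does not change.
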